ACIP acknowledged that the safety of Tdap immunisation during pregnancy has not been systematically studied, with the only data available coming from small studies, postmarketing surveillance, and the the US Vaccine Adverse Event Reporting System (VAERS).¹⁴ They concluded that *“available data from these studies did not suggest any elevated frequency or unusual patterns of adverse events in pregnant women who received Tdap and that the few serious adverse events reported were unlikely to have been caused by the vaccine.”*⁴

The NZ Ministry of Health’s Immunisation Technical Forum (ITF) on vaccines reviewed this recommendation in 2011 and has now recommended the use of Tdap during pregnancy in New Zealand (after 20 weeks).¹⁵ The Ministry of Health also recommends and funds (i.e the vaccine is given at no cost to the woman) influenza vaccination for all pregnant women in NZ.¹⁶

With this in mind, a District Health Board in Canterbury (CDHB) has agreed to fund the administration of Tdap during the current pertussis outbreak to pregnant women (30-36 weeks) and to women in the first 2 weeks after birth.¹⁷

For GPs to be paid for administering the vaccines they need to submit a correctly completed claim form to the CDHB. The usual practice is to submit the claim immediately after the vaccine is given and we would anticipate finding that a claim had been submitted within 1 week of its submission.

Study objectives

Primary Objectives:

- To describe adverse events in women who were administered Tdap between 30-36 weeks of gestation
- To describe outcomes of babies whose mothers were vaccinated with Tdap during week 30 to 36 of pregnancy (including birth history, weight and head circumference and any congenital abnormalities)

Secondary Objectives:

- To describe adverse events in women who were administered the seasonal influenza vaccine during pregnancy
- To describe adverse events in women who were administered the seasonal influenza vaccine and Tdap during pregnancy

¹³ United States Centers for Disease Control and Prevention. Updated recommendations from the Advisory Committee on Immunization Practices (ACIP). *MMWR* 2011; 60(41): 2011

¹⁴ US Advisory Committee on Immunization Practices. Summary Report. Atlanta, Georgia: ACIP; February 23-24, 2011. Available from <http://www.cdc.gov/vaccines/recs/acip/downloads/min-feb11.pdf> Accessed 23 April 2012.

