¹⁵ New Zealand Ministry of Health. Current advice on the public health management of pertussis. Wellington: MoH; 5 April 2012. Available at http://www.nzdoctor.co.nz/media/1682109/pertussis_letter_moh_5_apr_2012.pdf

¹⁶ New Zealand Ministry of Health. Chapter 15: Influenza. In Immunisation Handbook 2011. Wellington: MoH; 2011. Available at http://www.google.co.nz/url?sa=t&rct=j&q=ministry%20health%20influenza%20vaccine%20pregnant%20women%20funded%20&source=web&cd=7&ved=0CGYQFjAG&url=http%3A%2F%2Fwww.health.govt.nz%2Fsystem%2Ffiles%2Fdocuments%2Fpublications%2F15influenza.pdf&ei=8SiWT8iDH4_m8Q0gnNGMCg&usg=AFQjCNFUuAYDXQKxJFmtqXKd4PBfzm1i2A

¹⁷ Canterbury District Health Board. Media release from Canterbury DHB: Free whooping cough vaccine extended to pregnant women. Christchurch: CDHB; April 19, 2012.

- To compare adverse event rates in women who were vaccinated with Tdap, seasonal influenza vaccine or both
- To describe outcomes of babies whose mothers were vaccinated with the seasonal influenza during pregnancy (including birth history, weight and head circumference and any congenital abnormalities)
- To describe outcomes of babies whose mothers were vaccinated with the seasonal influenza and also received Tdap during weeks 30-36 of pregnancy (including birth history, weight and head circumference and any congenital abnormalities)
- To Evaluate infants of mothers vaccinated with Tdap, seasonal influenza vaccine or both during pregnancy who have symptoms consistent with pertussis or who have had significant contact with a proven case

Study design

This is a prospective observational cohort study. It will describe any adverse events in pregnant mothers who received either Tdap or influenza vaccine, or both. Outcomes for their infants will also be measured and described. Infants of mothers vaccinated with Tdap, seasonal influenza vaccine or both during pregnancy who have symptoms consistent with pertussis or who have had significant contact with a proven case will also be evaluated. The funded brands of Tdap are Boostrix and Adacel, and the funded brands of influenza are Fluarix and Fluvax).

Study population

Women vaccinated during pregnancy with Tdap will be identified through the GP record of claims for the administration of the vaccine as soon as possible after administration of the vaccine. Women from the same GP practices who have had trivalent inactivated influenza vaccine during pregnancy will also be identified and enrolled..

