It is possible women may have received Tdap from sources other than their GP e.g. healthcare workers or women who are seen at hospital with wounds that require a tetanus booster. However it is anticipated this will only be a very small proportion, and the records of claims through the CDHB will accurately reflect the total number of women in Canterbury receiving Tdap during pregnancy.

Identification of women receiving vaccination

Women will be identified as having received vaccination through the claims data submitted to the CDHB. The consent for for Tdap vaccine also asks women if they are happy to be contacted by the study team. Contact details will be obtained from their GP only for women who have indicated they are happy to be contacted.

Informed consent

The Claim form contains basic consent for participation in the study, but an additional consent form (Appendix 1) will be used to obtain signed informed consent for participation and handling of personally identifiable information and safety data.

If a woman chooses not to participate or to withdraw from the study at a later date the reason for non-participation or withdrawal will be recorded.

Confidentiality

Data will be collected and stored on a password protected database located in the Paediatric Department at Christchurch Hospital. The NHI will be used during data collection to identify study participants alongside a study identification number. The study identification number will not include any details that could potentially identify the study participant i.e. date of

birth. The NHI is included because it will provide the easiest access to information from GP records, particularly for newborn infants who may change surnames.

Prior to any data analysis the NHI will be removed from the database and just a study identification number will be used.

Expected sample size

The birth cohort in Canterbury is approximately 6000 per annum. Seasonal influenza vaccines are available in NZ between March and July. Both Tdap and influenza vaccine are funded for pregnant women, but it is very difficult to estimate how many women will take up the vaccines. As of 31st May 2012, 220 claims for the Tdap vaccine had been lodged with the CDHB in 6 weeks. At the 10th June, out of 255 claims processed 22 women had not consented to follow up. There were also a further 53 claims that have been rejected and returned to practices mainly as the consent yes or no was not completed.

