3-6 month check		Weight, head circumference, vaccination status, and standardised clinical examination by Plunket Nurse as recorded in Well Child book (Appendix 6). ³	
1-year follow-up		Final contact with mother about pertussis exposure and/or symptoms. Vaccination status – if not completed infant vaccinations by 6 months.	

¹ Three attempts will be made to contact mother by telephone within 1 week of notification of receipt of Tdap. If an e-mail address is available this will also be used if telephone contact is unsuccessful.

² Written questionnaire will be sent to mother before 4 weeks have elapsed since receipt of vaccine. Telephone contact will be made at 4 weeks of receipt of vaccine and two further times if the completed questionnaire has not been received within 1 week.

³ mothers will be encouraged to attend Plunket for checkups during the first 6 months. If there is no available recorded weight and head circumference between 3-6 months of age this will be done by a member of the the study team. The mother will be contacted 3 times via email or phone to get this information.

⁴ Three attempts will be made by phone or email to contact the mother each month

*Persistent cough lasting for >10 days and/or post-tussive vomiting

** Close contact defined as being in the same room as the person for > 1 hour or 5 minutes of face to face contact with a person with proven pertussis who was symptomatic.

Study instruments

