Appendix 8: Monthly surveillance questions for mother and infant

Reporting

It will still be the responsibility of the physician administering the vaccine to report any adverse events using the local reporting system.

The study team will also report any adverse events to:

- o Local pharmacovigilance agency (CARM – Centre for Adverse Events Monitoring, University of Otago, website: carm.otago.ac.nz)

Adverse Event and Serious Adverse Event Definitions

An Adverse Event (AE) shall mean any untoward medical occurrence whether thought to have been caused by the vaccines or not and Serious Adverse Event (SAE) shall mean any adverse event which is fatal, life threatening, disabling or incapacitating, requires in-patient treatment or prolongs existing hospitalization, is a congenital anomaly in the off-spring of the patient or which may require intervention to prevent the previously stated outcomes.

If there is a report of an unsolicited event during phone calls with the mother regarding pertussis symptoms in the baby- this will follow the same reporting as above.

Budget

	NZD
Research Nurse 0.5 FTE for 1 year	35,000
Research Nurse 0.5 FTE for 1 year	35,000
Database and statistical support	15,000
Publication and Reporting	3000
Consumables	1500
Total	89,500

Study Milestones:

July 2012	First participants enrolled in study	
December 2012	Last participants enrolled in study (this potentially may be extended depending on enrollment)	
July 2013	Interim report due	
December 2013	Last of the 1 year follow up data will be collected	
March 2014	Final study report due	
May 2014	Submission of publication	

Ethics Approval

The GP claim forms for administration of Tdap includes a section for the woman to indicate if she is willing or not to be contacted by researchers.

This study has been approved by Upper South A Regional Ethics Committee – approval **URA/12/EXP/021**.

Study Title: Safety Monitoring of Adverse Reactions to Tdap Vaccine in Pregnancy

Participants are identified by their NHI (National Health Index) number to prevent duplications and ensure only one survey per participant is possible. The NHI numbers are removed prior to data analysis.

Data collected at the practice will include:

GP Name of Practice where woman is enrolled PHONE	
Name of woman who received vaccination Address	
Contact phone number of woman Email	
NHI number (this is not to provide identification but only used to ensure that there are no duplications of surveys)	

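### Canterbury protocol (Study Three): enrolment opens as the influenza vaccine season closes and the one-week call rule names only Tdap, so the secondary Tdap/influenza/both comparison mixes vaccine effect with recall delay

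*Protocol*

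**What the plan says.** All references are to the Canterbury protocol, which is Appendix 8 of the Protocol, unless stated.

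- **Season.** Expected sample size: "Seasonal influenza vaccines are available in NZ between March and July".
- **Enrolment.** Study Milestones: July 2012 is the date for "First participants enrolled in study". December 2012 is the date for the last, with extension allowed.
- **Finding Tdap women.** Study population: they "will be identified through the GP record of claims for the administration of the vaccine as soon as possible after administration of the vaccine". Background: "The usual practice is to submit the claim immediately after the vaccine is given", with the claim expected to be found within about a week.
- **Finding influenza women.** Study population: "Women from the same GP practices who have had trivalent inactivated influenza vaccine during pregnancy will also be identified and enrolled". No interval from vaccination or notification is attached. Under the inclusion criteria the dose may fall at any stage of pregnancy.
- **First contact.** Study assessments and procedures, footnote 1: "Three attempts will be made to contact mother by telephone within 1 week of notification of receipt of Tdap". The table asks all mothers about 48-hour and 7-day events.
- **Four-week questionnaire.** Footnote 2 has it sent before 4 weeks have passed since the vaccine, without naming which vaccine.
- **Exclusion.** Women who have delivered before contact are not enrolled.
- **Use of the data.** Secondary Objectives: "To compare adverse event rates in women who were vaccinated with Tdap, seasonal influenza vaccine or both".

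**The concern.** The three study groups are asked the same questions, but the calendar does not let them be asked at the same distance from the dose. Tdap claims run through the enrolment period and trigger a call. Most influenza doses precede enrolment, and no rule sets how soon those women must be found. The same holds for the influenza dose of Group 3 women vaccinated separately.

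Mild and non-attended events are the ones most easily lost with time. A difference in reported rates between Tdap and influenza could then reflect interview timing, or a real difference could be hidden by it. The protocol itself expects subgroup differences to be small, so a modest artefact matters. In the main protocol, the Study Two procedures acknowledge reliance on recall for women contacted retrospectively (footnote 10). The Canterbury text has no handling for it.

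**Working it through.** **Scale.** The plan gives no figure for interview delay. Its precision figure reproduces: 2 × 1.96 × √(0.15 × 0.85 / 300) = 0.081, a half-width of about 4 points.

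**Assumptions (not in the documents).**
- Influenza doses are uniform over 1 March–31 July 2012, which is 153 days.
- Influenza gestation at vaccination is uniform over 12–36 weeks, or over the whole pregnancy.
- Tdap is given uniformly over 30–36 weeks from 19 April 2012 (31 May less the 6 weeks in which the 220 claims were lodged).
- Delivery is at T = 39 or 40 weeks.
- Contact is at the earliest possible date, with the opening taken as 1 July or 31 July.

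**Calendar alone.** 122/153 = 80% of influenza doses precede 1 July, and 94/153 = 61% are more than 4 weeks before it.

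**Influenza women still pregnant at contact.** With gestation 12–36 weeks, the chance of still being pregnant k days after the dose is (7T − 84 − k)/168, capped at 1. Summing over dose days:

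| Opening | T | Weight with k > 28 | Total weight | Share past 4 weeks |
|---|---|---|---|---|
| 1 July | 40 | 67.42 | 126.42 | 53% |
| 1 July | 39 | 63.51 | 122.34 | 52% |
| 31 July | 40 | 77.87 | 106.87 | 73% |
| 31 July | 39 | 72.70 | 101.53 | 72% |

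With gestation uniform over the whole pregnancy and T = 40, the chance is 1 − k/280. The shares are 68.65/126.20 = 54% and 83.92/111.47 = 75%. The range is therefore 52–54% for 1 July and 72–75% for 31 July. If uptake is front-loaded (declining linearly over the season), simulation with T = 40 gives 80–81% and 94–95%.

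**Tdap women, even enrolment to 31 December.** The chance of still being pregnant is (7T − 210 − k)/42, capped at 1, so it reaches zero at 63 or 70 days. In units of one day's vaccinations, the weight with k > 28 is 34 × 35 / (2 × 42) = 14.17 for T = 39 and 41 × 42 / (2 × 42) = 20.5 for T = 40. The whole pre-opening backlog is 41.5 or 48.5.
- 1 July opening (184 further days): 14.17/225.5 = 6% and 20.5/232.5 = 9%.
- 31 July opening (154 further days): 14.17/195.5 = 7% and 20.5/202.5 = 10%.

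**Tdap women, the 300 filled from the backlog first.** Claims run at 220/42 = 5.24 per day. With consent 233/255 this is 4.79 per day. The backlog is 4.79 × 41.5 = 199 or 4.79 × 48.5 = 232 women. Those past 4 weeks are 4.79 × 14.17 = 68 or 4.79 × 20.5 = 98, that is 23% or 33% of 300. This treats all claims as antenatal.

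**Gap.** Taking the same T and opening date in both groups, influenza exceeds Tdap by at least 53.3 − 32.7 = 20.6 points (1 July, T = 40, backlog filling). It exceeds it by at most 75.1 − 7.2 = 67.9 points (31 July, T = 39, whole-pregnancy gestation, even enrolment). The gap keeps its sign in every scenario.

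**Illustration of effect.** The recall loss is an assumption; the document gives none. Suppose the true rate is 15% in both groups and a fraction a of events is forgotten by women past 4 weeks. The false difference is 15 × a × gap. For a = 0.2 it is 0.6 to 2.0 points; for a = 0.4 it is 1.2 to 4.1 points.

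**The case against.** Several stronger readings are tempting, and the documents do not support them.

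- **That Tdap women are interviewed promptly.** About a week to find the claim plus a week of calls allows a 14-day lag. At that lag every Tdap woman is past 7 days at first contact. A contrast at 7 days appears only if the Tdap lag is assumed to be nil. The contrast that stands is the one at 4 weeks.
- **That the Tdap group is nearly free of delay.** By 10 June 2012, 255 claims had been processed and 22 women had declined, leaving 233, against a target of 300. Filling from that pool raises the late share to about 23–33%. Nurse-limited recruitment or postpartum claims would lower it. The document does not fix the pattern.
- **That no timing rule reaches influenza women.** First contact is to be made as soon as possible after identification for every mother, and footnote 2 is not limited to Tdap. However, identification of influenza women has no deadline, and footnote 2 cannot be met for doses given more than 4 weeks before July.
- **That the comparison is biased against Tdap by a known amount.** The recall loss is unsourced, no influenza sample size is stated, and most of the illustrated shifts lie inside the plan's own half-width of about 4 points. Pregnancy outcomes and medically attended events also come from the general practice at the 6-week check, and so do not rest on the mother's memory.
- **That the study's main aims fail.** The comparison is one secondary objective, reported descriptively with intervals within groups. The main protocol's Study Three objectives concern Tdap only.

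These points limit the size and reach of the concern. They do not remove the imbalance, which persists in every scenario tried.

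**Conclusion.** The point holds as a limitation of one secondary objective. On the stated July–December 2012 schedule, about half to three quarters of enrollable influenza women are beyond 4 weeks at the earliest possible contact. The Tdap share runs from under a tenth or so with even enrolment to at most about a third with backlog filling. The influenza range assumes uniform uptake; earlier uptake or later contact would raise it. Extending enrolment into the March–July 2013 season would lower it.

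Under-reporting of maternally recalled events in the influenza group, and for the separately given influenza dose in Group 3, is the likely direction. Its magnitude cannot be derived from the document. The primary descriptive aims for Tdap and the stated interval width are not affected.

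**What to change.** - Word footnote 1 so that the three call attempts within a week follow notification of either vaccine. This helps only women not yet interviewed; the main protocol describes Study Three as already in progress.
- Record the date of the first interview. Vaccination date is on the practice form, but no first-interview date field appears in the Canterbury forms shown, so confirm whether it was kept.
- Tabulate the delay from vaccination to interview by group, counted from each dose for Group 3 women vaccinated separately.
- Present the comparison of maternally reported events stratified by delay. Add a comparison limited to a common interval in all groups, for example interview within 4 weeks for the 48-hour and 7-day events and within 6 weeks for the 4-week events. Describe later-contacted women separately.

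The cost is a wording change, one date field to confirm and one derived variable. The restricted comparison will have a smaller, less precise influenza group: on the figures above, a 4-week limit keeps at best about 46–48% of influenza women for a 1 July opening and 25–28% for 31 July. A much tighter limit, such as 14 days, would discard most influenza women and some Tdap women, and is hard to defend as the main analysis.

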O09.2	14-19	Completed weeks
O09.3	20-25	Completed weeks
O09.4	26-33	Completed weeks
O09.5	34-36	Completed weeks
O09.9	Unspecified duration of pregnancy	

The yellow highlights are periods outside of the inclusion criteria.

Codes O09 should also have the following codes assigned for additional diagnoses:

Abortion	O00-007	Pregnancy with abortive outcome
Threatened abortion	O20.0	
Fetal death in utero	O36.4	
Premature rupture of membranes	O42	Before 37 completed weeks of gestation
Threatened premature labour	O47.0	False labour Before 37 completed weeks of gestation
Early onset of labour	O60	Early Preterm labour

Example

Patient admitted at 28 weeks gestation with a diagnosis of fetal death in utero (FDIU)

Medical and surgical induction of labour

O36.4	Maternal care for intrauterine death
O60.1	Preterm labour with preterm delivery
O09.4	Duration of pregnancy 26-33 weeks
Z37.1	Single stillbirth

1527- O48 will indicate prolonged pregnancy post dates and post term.

Some women deliver outside the hospital setting and this is estimated by the MoH at around 2%; however, information about these births is available via the National Maternity

Collection. All births, regardless of delivery setting, are assigned a unique National Health Index number. This allows capture of all post-birth hospital and/or notification events for all infants.

Inclusion criteria

Women

NZ women who are pregnant during the study period

Infants

Infants of the women who were pregnant during the study period

Study Two: Prospective intensive monitoring study of safety in pregnant women administered Tdap vaccination

This is a prospective observational study. It will describe any adverse events in pregnant mothers who received Tdap occurring within one month following immunisation. The data for this part of the study will be collected using the same methodology as that currently being used in Canterbury (i.e., Study Three currently in progress) and will therefore be directly comparable and also joint analysis will be possible for the maternal outcomes.

NOTE: We will not have any cases of spontaneous abortion in Studies Two and Three as the lower gestation eligible for vaccination and therefore inclusion in the study is 28 weeks.

Study population

All women vaccinated during pregnancy at any General Practice in NZ with Tdap vaccine will form the Study Two population.

Study participants

Study Two will include women 28–38 weeks pregnant.

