Funding for Tdap is being offered postpartum as well as during pregnancy, so women may choose to wait until their babies are born to take up the offer. Funding for the vaccine has approved for an initial period of 6 months with a view to extending for another 6 months if the pertussis outbreak continues. Previous outbreaks in New Zealand have lasted in the order of 18 months so it is likely that funding will continue beyond 6 months. We would therefore aim to enroll 300 women who have received Tdap vaccine.

Study groups

Group 1) received Tdap vaccine while pregnant (30 to 36 weeks gestation).

Group 2) received trivalent inactivated influenza vaccine while pregnant

Group 3) received both Tdap and trivalent inactivated influenza vaccine, separately or coadministered during pregnancy

Inclusion criteria

Women

- Pregnant women 18-40 years of age who have received either the Tdap vaccine between 30-36 weeks gestation, or received the influenza vaccine at any stage during pregnancy or both
- Compliant with routine antenatal care, including at least 1 ultrasound early in pregnancy
- Information regarding which brand vaccine of was given (if the brand is not available, batch number and expiry is sufficient as this will help to ascertain which brand was given)

Infants:

- Infants of the women who were vaccinated with the Tdap vaccine, seasonal influenza vaccine or both during pregnancy

Exclusion criteria

- Pregnant women who have received the Tdap vaccine prior to 30 weeks gestation or after 36 weeks gestation
- If a woman has already had her baby prior to being contacted by the the study team, she will not be enrolled in the study

Statistical Analysis

As this study is an observational study, the pregnancy outcomes and safety data will be descriptive in nature. The rates of AEs and SAEs will be compared to published background rates for the general population (summarised in Tavares et al¹⁰). The expected rates of MAEs and SAEs for Tdap given during pregnancy is unknown, but as a guide the rates of MAEs for pregnant women receiving influenza vaccine in this paper ranged from 1.1 to 3.8% while the rate of SAEs ranged from 0.4 to 1.5%. Where the known background incidence of 0.01 for a particular adverse event, a sample size of 300 achieves 80% power to detect an additional incidence rate of 0.0175 when the significance level is 0.05.

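### Appendix 8 compares maternal adverse event rates between Tdap at 30–36 weeks and influenza vaccine at any gestation, so gestation-dependent events are confounded, and Group 3 mixes one and two post-dose windows

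*Protocol*

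**What the plan says.** All of this is in Appendix 8 (Canterbury Protocol) unless noted.

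- **Secondary Objectives:** "To compare adverse event rates in women who were vaccinated with Tdap, seasonal influenza vaccine or both".
- **Inclusion criteria:** women who had "Tdap vaccine between 30-36 weeks gestation, or received the influenza vaccine at any stage during pregnancy or both". The exclusion criteria remove Tdap given before 30 or after 36 weeks. They set no gestational limit for influenza vaccine.
- **Study groups:** Group 1 is defined by Tdap at 30–36 weeks. Group 2 is defined by influenza vaccine, with no gestation stated. Group 3 takes in every woman who "received both Tdap and trivalent inactivated influenza vaccine, separately or coadministered during pregnancy".
- **Study assessments and procedures:** solicited events are captured at 48 hours, 7 days and 4 weeks after vaccination, whichever vaccine was given. The list of data asked of the woman refers to the period after each dose.
- **4-week written questionnaire (Appendix 5 within Appendix 8):** it includes spontaneous or threatened abortion, severe nausea or vomiting, premature labour, premature membrane rupture and new-onset hypertension.
- **Statistical Analysis:** descriptive, with a confidence interval for each group's proportion. Stratification or alignment by gestation or dosing pattern is not mentioned.
- **Main protocol, Study Two:** "We will not have any cases of spontaneous abortion in Studies Two and Three as the lower gestation eligible for vaccination", the stated reason being a 28-week lower limit.

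**The concern.** An objective worded as a comparison invites the reader to take a difference between groups as a difference between vaccines. Here the group definitions build in a second difference, the stage of pregnancy at vaccination. Four weeks after a first-trimester influenza dose and four weeks after a Tdap dose at 30–36 weeks expose a woman to different obstetric events.

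Tdap could look safer on early-pregnancy items and worse on late-pregnancy items with no vaccine effect at all. The Group 3 rate would also depend on how many of its women had their doses on the same day, which is not a property of either vaccine.

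**Working it through.** **1. The groups side by side**

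| | Gestation at vaccination | Pregnancy must have lasted to | 4-week post-dose windows |
|---|---|---|---|
| Group 1 (Tdap) | 30–36 weeks | the Tdap dose | one |
| Group 2 (influenza) | any | the influenza dose | one |
| Group 3 (both) | Tdap 30–36 weeks; influenza any | the Tdap dose | one if same day, two if separate |

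A woman given influenza vaccine early enters Group 3 only if she is still pregnant in the Tdap window. A loss or birth before 30 weeks that follows vaccination can therefore fall only in Group 2. Part of the contrast is survival to the Tdap window.

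**2. The plan's own figures** (Statistical Analysis)

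- Power for a background rate of 0.01, an added 0.0175 and n = 300, one-sample normal approximation: Φ[(0.0175 − z·√(0.01·0.99/300)) / √(0.0275·0.9725/300)]. With z = 1.645 this is Φ[(0.0175 − 0.00945)/0.00944] = 80.3%, which reproduces the stated 80%. Two-sided (z = 1.96) it is 74.6%.
- Interval width at a proportion of 0.15: 2·1.96·√(0.15·0.85/300) = 0.081, as stated.

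Both figures describe a single group of 300. Neither concerns a comparison between groups.

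**3. How much of Group 2 is unmatched** (assumption, not a document figure)

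The documents give no distribution of influenza doses over gestation. If doses were spread evenly:

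- over weeks 5–40, 7/36 = 19% fall at 30–36 weeks, leaving about 81% unmatched;
- over weeks 14–40, 7/27 = 26% do, leaving about 74% unmatched.

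**4. One window against two in Group 3**

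Assume no vaccine effect, a constant background risk r per 4-week window, and two windows that do not overlap. The risk over both is 1 − (1 − r)². For r, take the range of medically attended event rates that the protocol cites as a guide, 1.1% to 3.8%; applying it per 4-week window is an assumption.

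- r = 1.1%: 1 − 0.989² = 2.2%
- r = 3.8%: 1 − 0.962² = 7.5%

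That is about twice the risk of same-day dosing. Overlapping windows would reduce the ratio.

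**5. Where observation time is equal**

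After a single dose the solicited windows have the same length in Groups 1 and 2 (ratio 1.0). Apart from separate dosing, time is unequal only at the 6-week check, where medically attended maternal events are collected since the last contact. With birth at 40 weeks (assumed), vaccination to that check takes 46 − g weeks: 34 for g = 12, 26 for g = 20 and 13 for g = 33.

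**The case against.** The strongest reply is that little rests on this comparison. It is one secondary objective of an appended, already approved study. The analysis is descriptive, no between-group test is specified, and gestational strata are often left to an analysis plan. This stands as a limit on importance. It does not remove the point, because the group definitions and the word compare are already fixed in the protocol.

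Several stronger readings are tempting and are not supported:

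- *Gestation and observation time, not the vaccine, determine the result.* Solicited windows are equal after a single dose, and nothing suggests that gestation dominates local reactions or fever in the first days. Only confounding of gestation-dependent items is shown.
- *Separate dosing must give a much higher event rate.* A reader might combine the single-vaccine unsolicited rates in Related research as if independent. The same section reports similar reactogenicity for sequential and co-administered dosing, with unsolicited events in about 20% of both groups. Those were adults aged 19–64, not identified as pregnant, but the report argues against a firm prediction. The factor of two is an upper illustration for background events.
- *Most of Group 2 is known to be unmatched.* The 74–81% share is assumed. Influenza vaccine is available March to July, enrolment opens in July 2012, and the exclusion that begins "If a woman has already had her baby prior to being contacted by the the study team" also shapes who enters.
- *Infant outcomes are affected too.* The infant objectives describe or evaluate outcomes; they do not compare groups.
- *The spontaneous abortion statement is wrong.* It is right for the Study Three of the main text, which covers Tdap recipients only. The influenza groups appear only in Appendix 8, so this is a matter of scope.

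The exclusion of complicated pregnancies from the final analyses might remove some listed events. The term is undefined, so it cannot be counted on to align the groups.

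**Conclusion.** The point holds for the maternal adverse event comparison in Appendix 8. Groups 1 and 2 differ in gestation at vaccination, and Groups 1 and 3 require survival of the pregnancy to the Tdap window. Differences on gestation-dependent items of the 4-week form therefore cannot be attributed to the vaccine, in either direction. Short-term local reactions and fever are much less affected.

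Pooling in Group 3 can add up to about a twofold difference in background-event risk between separate and same-day dosing, given non-overlapping windows, a constant background rate and no vaccine effect. The actual size depends on the gestation mix and the share co-administered, neither of which the documents give. The primary objectives, the main-text objectives for Study Three and the infant descriptions are unaffected.

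**What to change.** In Appendix 8, Secondary Objectives, Study groups and Statistical Analysis:

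1. For the maternal comparison only, restrict influenza doses to those given at 30–36 weeks, or stratify by gestation at vaccination. Describe influenza doses given earlier in pregnancy separately.
2. Report Group 3 as same-day and separate dosing, with a 4-week window tied to each dose. This also keeps the open-ended 6-week interval out of the comparison.
3. Confirm that the date of each separate dose is recorded. The practice form lists the due date, one date of vaccine administration and concomitant vaccines, with no dedicated date for a separate influenza dose.
4. In the main protocol's Study Two section, state that the note on spontaneous abortion refers to Tdap recipients.

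Most of the data needed are already collected, so the change is largely one of wording. The price is a smaller matched influenza group and wider intervals. At a proportion of 0.15 the width rises from 0.081 at n = 300 to 0.114 at n = 150 and 0.140 at n = 100. These sizes are illustrative, since the protocol sets a target only for Tdap recipients.
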